## **9.2 Statistical methods**

Comparisons of arterial stiffness and arterial wave characteristics between the placebo and beetroot juice visits will be performed using paired t-tests. Paired t-tests will also be performed to compare plasma nitrate and nitrite concentrations between the two visits for all data points. Two-factor ANOVA with repeated measures will be used to assess blood pressure lowering effects of beetroot juice at rest and during exercise in postmenopausal women. A value of  $p < 0.05$  will be considered statistically significant for all experiments.

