## 1.0 Objectives

### 1.1 Study Objectives

The proposed study aims to evaluate the acute vascular effects of dietary nitrates on the peripheral and central circulation, both at rest and during physiological stress in older women.

**Aim 1:** To determine the blood pressure-lowering effects of acute dietary nitrate supplementation in postmenopausal women.

*Hypothesis: A one time dose(140 mL) of concentrated beetroot juice will lower resting arterial stiffness, brachial artery blood pressure, and/or derived aortic blood pressure in postmenopausal women with and without hypertension.*

**Aim 2:** To determine the effects of acute dietary nitrate supplementation on myogenic vasoconstriction of leg blood vessels during simulated postural stress.

*Hypothesis:* A one time dose (140 mL) of concentrated beetroot juice will reduce the amount of vasoconstriction in leg blood vessels exposed to graded increases in vascular transmural pressure (i.e., single leg suction) in postmenopausal women with and without hypertension.

**Aim 3.** To determine the effects of acute dietary nitrate supplementation on the control of blood pressure responses during exercise.

*Hypothesis:* A one time dose (140 mL) of concentrated beetroot juice will lower blood pressure responses to static arm and dynamic leg exercise. Beetroot juice will reduce the concentration of blood pressure-raising metabolites in exercising muscles through improvements in muscle perfusion and/or reductions in the metabolic cost of muscle contraction.

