### **1.2 Primary Study Endpoints**

The primary endpoints of this study are blood pressure, arterial wave reflection characteristics, and muscle metabolic responses. These responses will be measured at rest and during exercises in postmenopausal women before and after beetroot juice consumption.

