- 6) Dynamic Leg Exercise (DLE) - While seated in semi recumbent position, participants will have one leg placed in a knee-exercise device. We will then passively move their leg for them in a kicking motion while a cuff is inflated on their upper thigh. Participants will then perform 9 minutes of active knee extensions (3 min no resistance; 6 minutes moderate resistance) with the thigh cuff deflated, followed by 3 minutes of rest with the cuff inflated. Leg blood flow will be measured by Doppler ultrasound, and muscle pH will be measured by a near-infrared sensor placed over the skin on the thigh.

Premenopausal Visit 3. Estradiol assessment visit (Premenopausal women only). – Subjects will be asked to return to the lab on one day between days 9-11 of their menstrual cycle for a blood draw. Approximately 10 ml of blood will be taken from an arm vein during this visit. This blood draw will be used to assess their serum estradiol content at that point in their cycle. The results of this test will be used to schedule their second experimental visit (Premenopausal visit 4). Subject visits will be scheduled so that no more than 2 blood draws occur in a given week.

Postmenopausal Visit 3. Beetroot Juice Study Visit (Postmenopausal women only) - A CRC nurse will take a blood sample from an arm vein. Participants will then undergo measures of HR, PWV, and BP. Next, participants will consume 140 mL (9.5 tablespoons) of either nitrate-rich beet juice or beet juice with nitrates removed with a small snack, and will remain at the CRC

for 1.5 hours. 1.5 hours after consuming the beet juice, a second blood sample will be taken and the participants will undergo measures of HR, PWV, BP, LS, SHE, and DLE. Once these measurements are completed, a third blood sample will be taken.

Premenopausal Visit 4. Experimental Study Visit- Procedures will be identical to those during Premenopausal Visit 3.

Postmenopausal Visit 4. Beetroot Juice Study Visit (Postmenopausal women only) - Procedures will be identical to those during visit 3 except that participants will consume whichever drink supplement they did not receive during visit 3.

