#### **7.4.5 Blinding of the Test Article**

Treatment order will be randomly assigned to participants by Clinical Research Center (CRC) staff using computer-based mathematical software (Microsoft Excel). The generated list that determines each participants treatment order will be kept in a secure location in the CRC which cannot be accessed directly by research team members.

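### Section 9.2 compares the two juice visits of a randomised crossover by paired t-tests with no visit-order term, and 7.4.5 does not require the two orders to be balanced; this matters only if levels are compared and responses shift between visits

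*Combined protocol and SAP*

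**What the plan says.** The postmenopausal part is a two-period crossover. Under 7.2.2, at Visit 4 "participants will consume whichever drink supplement they did not receive during visit 3". The only statement on assignment is in 7.4.5: "Treatment order will be randomly assigned to participants by Clinical Research Center (CRC) staff using computer-based mathematical software (Microsoft Excel". It mentions no blocking, no equal numbers per order and no stratification. Section 7.4.3, on the method of assignment, is marked as not applicable.

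Section 9.2 gives two kinds of analysis:
- For stiffness and wave outcomes: "Comparisons of arterial stiffness and arterial wave characteristics between the placebo and beetroot juice visits will be performed using paired t-tests". Plasma nitrate and nitrite are also compared between the visits by paired t-tests, at every sampling point.
- For blood pressure: "Two-factor ANOVA with repeated measures will be used to assess blood pressure lowering effects of beetroot juice at rest and during exercise". The two factors are not named.

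No period or order term appears in either. Section 9.2 does not say whether stiffness and wave outcomes are compared as post-dose values or as change from the same day's pre-dose value. It names no analysis for leg suction or muscle metabolism.

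The measurement schedule in 7.2.2 decides which outcomes are exposed. Before the drink: "Participants will then undergo measures of HR, PWV, and BP. Next, participants will consume 140 mL (9.5 tablespoons". After it: "the participants will undergo measures of HR, PWV, BP, LS, SHE, and DLE". Heart rate, pulse wave velocity (PWV) and blood pressure therefore have a same-day pre-dose value, as does the blood sample. Leg suction and both exercise tests do not. Wave characteristics are not named before dosing, although they may come with the blood pressure measurement. Section 1.2 allows a change reading: "These responses will be measured at rest and during exercises in postmenopausal women before and after beetroot juice consumption".

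**The concern.** In a two-period crossover, the difference between the drinks within one woman is also a difference between two visits. If responses drift from Visit 3 to Visit 4, for example through habituation, each woman's beetroot-minus-placebo difference contains that drift, with a sign set by her order. A plain paired t-test treats it as noise when the orders are equal, and leaves part of it in the estimate when they are not. An order term removes it in both cases.

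The stake is power in a very small trial and, for the single trial actually run, an estimate displaced by a known fraction of the drift. It concerns any paired comparison made on levels. That covers plasma nitrate and nitrite as 9.2 is written, and stiffness and wave outcomes if they are compared post-dose.

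**Working it through.** The plan gives no visit shift and no order split, so it has no figure of its own to reproduce here.

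**Inputs from the documents.** Two visits per woman in random order (7.2.2, 7.4.5); six per group (9.1); normotensive and hypertensive postmenopausal women (4.1); alpha 0.05 (9.2), taken as two-sided.

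**Assumed.** SD units of a single-visit measurement; true effect -0.5; between-visit correlation rho = 0.6 (range 0.4 to 0.8); shift 0, 0.25 or 0.5; n = 6 (one group) or 12 (two groups of six). Section 16.0 gives 24 as the minimum number of completers without a split by group, so the number of postmenopausal women is not fixed by the documents.

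**Model.** For woman i, d_i = beetroot minus placebo = effect + shift × o_i + error, with o_i = +1 if beetroot comes second and -1 if first. The error variance is 2(1 - rho) = 2 × 0.4 = 0.8.

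**Step 1: equal orders.** The plain mean of d is unbiased, but the sample variance of d has expectation 0.8 + shift² × n/(n-1). At n = 12 and shift 0.5 this is 0.8 + 0.25 × 12/11 = 1.073. The test then uses a standard error of about √(1.073/12) = 0.299 instead of √(0.8/12) = 0.258. Power (order-adjusted from the noncentral t; plain with a shift by simulation):

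| n | shift | plain | order-adjusted |
|---|---|---|---|
| 12 | 0 | 0.42 | 0.42 |
| 12 | 0.25 | 0.39 | 0.42 |
| 12 | 0.5 | 0.31 | 0.42 |
| 6 | 0 | 0.20 | 0.19 |
| 6 | 0.25 | 0.18 | 0.19 |
| 6 | 0.5 | 0.13 | 0.19 |

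To three decimals, the no-shift pairs are 0.424 and 0.417 (n = 12) and 0.201 and 0.186 (n = 6). At n = 12 and shift 0.5, the pair is 0.24 and 0.30 at rho 0.4, and 0.48 and 0.69 at rho 0.8. At rho 0.6 the order term starts to gain power at a shift between 0.10 and 0.15 SD for n = 12, and at about 0.2 SD for n = 6.

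**Step 2: unequal orders.** With n1 women taking beetroot second and n2 first, the mean of d is effect + shift × (n1 - n2)/n. At 8:4 the fraction is 4/12 = 1/3. With a 0.5 SD shift the plain estimate is -0.5 + 0.167 = -0.33, or -0.67 if the larger order is the other one. The order-adjusted estimate is -0.50 in both cases.

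If the list were unrestricted, which 7.4.5 does not say, a split of 8:4 or worse among 12 would have probability 0.39, and 4:2 or worse among six would have probability 0.69.

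**Step 3: type I error of the plain test, n = 12.** Averaged over all random orders it is 0.050 to 0.052 for shifts of 0.25 SD to one SD of the paired difference. Given the realised split, with a 0.5 SD shift, it is 0.026 at 6:6, about 0.056 at 8:4 and 0.10 at 9:3. A split of 9:3 or worse has probability 0.15 on an unrestricted list.

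**Step 4: which contrasts are exposed.** A shift that is constant within a visit cancels from post-dose minus same-day pre-dose, from a drink-by-time interaction, and from stress minus rest at the same visit. It does not cancel from a comparison of levels. Subtracting the Visit 2 battery does not help, because that one value is shared by both drinks.

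**The case against.** The case against is strong on where the harm falls. The resting outcomes that 9.2 gives to paired t-tests mostly have same-day pre-dose values, and a change contrast would already remove a constant shift. The outcomes with no pre-dose value at the juice visits are not given to a paired t-test at all. This stands.

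A reader might infer that Aim 3 is exposed because exercise is performed only after the drink. The documents do not support that. The hypothesis is that beetroot juice "will lower blood pressure responses to static arm and dynamic leg exercise", which can be read as a rise from rest at the same visit, and post-dose resting blood pressure is measured at that visit. Leg suction alternates with rest in the same way. For these outcomes only a comparison of levels, or a shift in reactivity itself, would be affected.

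A reader might also infer that the paired t-test is invalid, that the list is unrestricted, or that a shift is to be expected. The first is wrong over randomisations (Step 3). On the second, 7.4.5 is silent. On the third, familiarisation at Visit 1, the full battery at Visit 2, the pre-visit restrictions and the spacing of at least 5 days (7.2.1, 7.2.2, 7.3) all work against a shift.

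Finally, the gain is small for a modest shift: 0.02 to 0.03 of power at 0.25 SD and n = 12, and almost nothing at n = 6. That also stands. What remains is that these safeguards make a shift less likely but do not protect a comparison of levels if one occurs.

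**Conclusion.** The point holds as a cheap improvement. It does not invalidate the planned tests. Section 9.2 omits a term that the design supplies at little cost, and 7.4.5 leaves the balance of orders open. If there is a visit shift and levels are compared, the loss at n = 12 is about 0.03 of power for a 0.25 SD shift and 0.11 for 0.5 SD with equal orders. With unequal orders, (n1-n2)/n of the shift enters the estimate. If there is no shift, or the contrast is a same-day change or a rest-to-stress response under a constant shift, there is no such harm.

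The wording of the plan and the fraction formula are certain. The power figures rest wholly on the assumed effect, correlation, shift and number of women. Whether the blood pressure ANOVA already includes period cannot be told, because its factors are unnamed.

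**What to change.** Make two changes together.

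1. In 7.4.5, have the Clinical Research Center generate the order list in permuted blocks so that the two orders are balanced. Do this within blood pressure group only if the plan's own group definition is available at assignment. Sections 3.1 and 3.2 give no cut-off separating normotensive from hypertensive postmenopausal women.
2. In 9.2, replace the plain paired t-test by its order-adjusted version: regress the beetroot-minus-placebo difference on order coded +1/-1 and test the intercept by t on n - 2 degrees of freedom. Include period in the blood pressure ANOVA where levels are compared.

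Blocking alone does not rescue the plain test: with 6:6 and a 0.5 SD shift its power is still 0.31. Adjusting an unblocked list that falls 8:4 costs about 0.04 of power at n = 12 if there is no shift (0.42 to 0.38).

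Cost: wording in two sections, a blocked list in the same software and no new measurement. The price is one error degree of freedom. With equal orders, no shift and rho 0.6, that is about 0.01 of power at n = 12 and 0.015 at n = 6. Whether each resting outcome is compared as a post-dose value or as a change should also be stated, but that is a separate matter of pre-specification.

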## **10.0 Confidentiality, Privacy and Data Management**

### **10.1 Confidentiality**

Confidentiality will be maintained with all data collected. Participants will be assigned an identity code that will be used to identify all data collected during the study. The identity code will be only known by study personnel and will not contain any information that can be used to identify the participant. Paper and computer forms of data will be stored within a specific study binder and on a dedicated research laboratory computer, respectively. The study binder is always stored within the laboratory and the laboratory door is locked outside of work hours. The research computer is located inside the laboratory and cannot be accessed unless a correct username and password is provided.

#### **10.1.1 Identifiers associated with data and/or specimens**

There will not be a direct identifier associated with data and/or specimens.

##### **10.1.1.1 Use of Codes, Master List**

The list linking the code numbers to participants will be created and stored in a secure file cabinet, the password-protected lab computer inside of the Vascular Aging and Exercise Laboratory (201 Noll Laboratory) which will also be locked when not occupied by lab personnel. The list linking code numbers to participants will be destroyed within 5 years of completing data collection.

#### **10.1.2 Storage of Data and/or Specimens**

Data collected for this study will be stored in Noll 201 for hard-copies and password-protected folders on the secured PSU server for electronic copies.

Plasma samples from the study visits will be stored in a low-temperature freezer located in 118 or 120 Noll Laboratory.

Daily urine samples used to assess estrogen exposure will be stored in -20 freezers. These freezers are located in room 124, room 121, room 116, room 117, room 2, room 3, and in the basement hallway in Noll Lab. Samples will be destroyed within one year of enrollment in the study.

#### **10.1.3 Access to Data and/or Specimens**

Only members of the Vascular Aging and Exercise Laboratory and co-investigators approved on this protocol will have access to the data.

#### **10.1.4 Transferring Data and/or Specimens**

Approximately 1 ml of plasma from each blood sample will be sent to [name] at Wake Forest University for measurement of plasma nitrate/nitrite concentrations. The frozen samples will be shipped overnight.

Approximately 5 ml of blood will be given to [name] [name], also located in Noll lab, for measurement of serum estradiol concentrations. The frozen samples will be stored in the freezers located in the lab of [name] [name] in Noll laboratory (rooms 2, 117, 121).

## **10.2 Privacy**

Throughout the study duration, researchers will maintain a professional manner. Regarding health and/or personal information, researchers will only obtain this information via questionnaires and lab results. Moreover, researchers will only discuss this information with participants as it relates to their participation in the study (i.e., their eligibility). Participants will also be reminded that any information that they provide is voluntary, and can refuse to provide any information they wish.

During the study visits, subjects' privacy will be maintained by performing all procedures in a private laboratory room(s). These rooms will be shut during all study visits, and will not be visible to persons in the building corridors.

# **11.0 Data and Safety Monitoring Plan**

## **11.1 Periodic evaluation of data**

Not applicable

## **11.2 Data that are reviewed**

Not applicable

## **11.3 Method of collection of safety information**

Not applicable

## **11.4 Frequency of data collection**

Not applicable

## **11.5 Individual's reviewing the data**

Not applicable

## **11.6 Frequency of review of cumulative data**

Not applicable.

## **11.7 Statistical tests**

Not applicable.

## **11.8 Suspension of research**

If abnormal physiological responses to any part of the protocols or dietary nitrate supplementation are observed, the research will be suspended immediately.

# **12.0 Risks**

Blood Sampling - This may cause some mild discomfort and bruising where the needle is inserted into the arm. There is also a very small risk of developing an infection or a clot at the insertion site.

Step-based Fitness Test - During the exercise test, participants may experience muscle fatigue, shortness of breath, or a side cramp. It is also possible to experience light-headedness, chest discomfort, or irregular heartbeats during this test. There is also a small risk of participants losing their balance and/or falling during the test.

Heart Rate - It is possible that the adhesive on the sticky electrodes may irritate participants' skin. There is also a minimal risk that an allergic reaction could occur from the adhesive.

Blood Pressure/Pulse Wave Velocity - During inflation of the cuffs, participants may feel a numb and/or tingling sensation in their hands/feet that will go away quickly after the cuffs are deflated. During the pulse wave velocity test, they may also experience some temporary discomfort (pressure) while the researcher holds a small sensor over an artery in their neck.

Leg Suction - During the suction participants feel temporary sensations of swelling in their leg. There is also a small risk that they may experience temporary feelings of light-headedness. The vacuum will tend to pull participants' legs leg into the box, and as a result they may feel a moderate pressure pushing against their upper thigh.

Doppler Ultrasound - There is a minimal risk that the ultrasound probe and/or gel will irritate participants' skin. Participants may feel minor discomfort (pressure) when the researcher is pressing the ultrasound sensor against their upper arm or upper thigh.

Near-Infrared Spectroscopy - There are no known risks associated with use of the near-infrared device. However, it is possible that the adhesive on the sticky plastic sensor may irritate the skin.

Static Arm Exercise - Participants may feel temporary fatigue in the muscles of the exercising arm. It is also possible to experience soreness in these muscles within 24-48 hours following this study visit. There is a small risk that participants may develop a bruise from the inflation of the cuff on the upper arm. It is also possible to experience a numb, tingling sensation in the arm while the cuff is inflated. There is also some risk of the appearance of petechia (small pink blotches on the skin) as a result of the increased venous blood pressure in the occluded forearm during exercise. If present, these very small pink dots may persist for several days but are not associated with any pain or long term adverse effects.

Dynamic Leg Exercise - Participants may feel temporary muscle fatigue in the thigh muscles of the exercising leg. It is also possible to experience soreness in these muscles within 24-48 hours following this study visit. There is a small risk that participants may develop a bruise from the inflation of the cuff on the upper thigh. It is also possible to experience a numb, tingling sensation in the leg while the cuff is inflated.

Consumption of beet juice - There are no known health risks associated with consumption of nitrate-rich beet juice, a commonly sold health drink/supplement in Europe. The most common side-effect of beet juice consumption is pinkish-colored urine (known as "beeturia") and/or stool. This can occur after consuming either the nitrate-rich or placebo version of the drink.

## **13.0 Potential Benefits to Subjects and Others**

### **13.1 Potential Benefits to Subjects**

Postmenopausal participants will receive more regular monitoring of their resting blood pressure. Throughout the duration of the study protocol, participants will have their untreated blood pressure measured by trained research personnel on 4 separate occasions, and these measurements will be provided at no cost to them and/or their insurance provider. Postmenopausal participants will also be provided information about their aortic blood pressure, a measurement which may have more predictive value for future cardiovascular events than arm blood pressure measurements alone. With patient

permission, all blood pressure-related information will be shared with their primary care physician.

There are no direct benefits to premenopausal women for participating in this study other than receiving information about their cardiovascular risk factors (i.e., blood pressure, blood cholesterol, fitness level, etc.).

### **13.2 Potential Benefits to Others**

This research may further our understanding about the potential for nitrate-rich food/dietary supplements to help control blood pressure without (or with less) medication(s) in a population with increased blood pressure-related cardiovascular risk (i.e., postmenopausal women).

## **14.0 Sharing Results with Subjects**

In the event that abnormal lab test results are obtained during initial screening or subsequently throughout this study, the subjects will be informed as quickly as possible of these results and instructed to contact your private physician for further assessment. The lab test results will be made available to your private physician at your request.

Individual data will be shared with the subjects upon requests. However, the study results will not be shared until the data are published (e.g. journal articles).

